6.3 Special Instructions and Definitions of Evaluations

6.3.1 Consent: The informed consent process will occur during pre-screening, and must be completed prior to screening VOG testing. A signature on the consent form does not translate into enrollment in the study. Only after informed consent has been signed **and** all relevant inclusion/exclusion criteria have been met can a patient be randomized or enrolled in the observational arm of the study.

Informed consent must be obtained from the patient. Patients will not be enrolled if consent cannot be obtained. The study center will document the informed consent process and the signing of the consent form in a written progress note, place a signed copy of the consent form in the hospital medical record, and keep the signed original consent form in the study subject file. A signed copy must be given to the subject as well. The study monitor will review and confirm the signed consent form while reviewing subject data collection forms and/or during monitoring visits (which may be conducted remotely or on site).

6.3.2 Structured Symptom History: SCs will gather standard identifying, demographic, and meta-data (e.g., triage severity); key clinical parameters related to dizziness (e.g., symptom onset, timing, triggers, type⁴²), associated symptoms (e.g., tinnitus, hearing loss, other neurological symptoms), and key past medical history.

6.3.3 Vertigo Symptom Scale – short form (VSS-SF¹⁶⁶): The VSS-SF incorporates two sub-scales with 8 items relating to vertigo-balance and 7 items relating to autonomic anxiety symptoms. Severe dizziness is defined as ≥12 points on the total scale. Subjects will complete the VSS-SF at baseline and 1-month visit.

6.3.4 ABCD² Vascular Risk Score¹⁶⁷: The ABCD² score will be calculated to determine the risk for stroke in the days following the ED index visit. This measure will likely be incorporated into the initial diagnostic algorithm.

6.3.5 NIH Stroke Scale (NIHSS): The NIHSS will be done by a certified examiner during screening or shortly after randomization and then repeated at the 1-week visit.

6.3.6 Scale for the Assessment and Rating of Ataxia (SARA): SARA is an 8-item clinical scale that will be used to assess cerebellar signs. The scale assesses gait, stance, sitting, speech, finger-chase test, nose-finger test, fast alternating movements, and heel-shin test. The SARA evaluation will be done during screening or shortly after randomization and then repeated at the 1-week follow-up visit.

6.3.7 Calibrated Finger Rub Auditory Screening Test (CALFRAST): CALFRAST is a rapid bedside assessment for hearing loss using finger rubbing. Results of this test at the ED Index Visit will be used as part of the diagnostic algorithm. The test will be followed post-randomization by portable audiology in the ED to confirm the accuracy of the clinical assessment. We will obtain formal, lab-based audiology at 1-week follow-up, in addition to repeating the CALFRAST test during the follow-up bedside exam, for comparison to audiology.

6.3.8 Subjective Visual Vertical (SVV): Measurement of the patient's SVV is a routine part of bedside and laboratory vestibular testing. This psychophysical test assesses the patient's perception of verticality. At the ED Index Visit, testing will be accomplished using a standard 'bucket test.'¹⁷⁴ In the bucket test, the examiner holds a large bucket in front of the patient's face so that they are peering at the floor of the bucket. A straight line is displayed in the floor of the bucket. As the examiner rotates the bucket slowly, the patient is asked to notify the examiner when they believe the line to be completely vertical (i.e. parallel to gravity). The bucket is pre-calibrated, and the examiner records how far from true vertical the bucket line is when the patient believes the line is vertical. The test will be repeated at the 1-week follow-up. Depending on site-specific procedures, tests may be performed using the bucket, a mechanical light bar (see Laboratory-based vestibular testing), or both.

6.3.9 Portable VOG – HINTS-Hallpike: Using the ICS Impulse 3-dimensional VOG (horizontal-vertical-torsional channels), trained SCs will record eye movements, including VOR gain (horizontal head impulses); nystagmus—spontaneous (with, without fixation), gaze-evoked, positional (Dix-Hallpike [Nylen-Bárány] plus supine roll positional tests⁵⁰), head shaking¹⁰⁴; and eye alignment (alternate cover for skew deviation⁶⁰).

As per standard practice, testing will occur under conditions of visual fixation and with vision denied. Vision will be denied using the manufacturer's FDA-approved disposable occluder and eyepatch or a study-designed drape affixed to a simple plastic headband. The manufacturer's disposable vision denied solution is comprised of one sticky patch that is fully opaque for the non-test (left) eye and a cup inserted into the goggles frame that allows the infrared camera to record eye movement in the recording (right) eye. Both pieces have a mild adhesive backing and are applied to the orbital rim of each eye. The materials have passed biocompatibility testing. After testing, the patches are gently removed by slowly releasing the adhesive from the skin. The study-designed external drape is intended to speed testing during recruitment by eliminating the need to remove the goggles, affix the adhesive patches, replace the goggles, recalibrate, and then remove the adhesive patches.

During testing, we will record video images of the eye movement examination for the following purposes: (1) final diagnosis adjudication for the main trial outcome of diagnosis accuracy; (2) monitoring adherence to trial examination protocols; (3) additional research questions (e.g., concordance between expert eye movement interpretation and results of quantitative recordings and algorithmic interpretation; assessing head tilt and ocular counter-roll as signs of central vs. peripheral disease); and (3) generating an educational library of teaching videos, as articulated in the AVERT grant proposal. Images will include the following: eye-only videos (non-

identifiable), room camera videos of most test procedures (potentially identifiable), partial-face close-up eye movement exams (potentially identifiable), and full-head/face images for head tilt (identifiable).

Identifiable images will only be used outside the research study team (e.g., for education or academic publication) if the subject elects this option when signing the consent.

6.3.10 Portable Audiometry: SCs will use portable audiology headphones to record hearing in each ear (air and bone conduction thresholds). SCs will be properly trained in hearing testing and assessment (e.g., conductive vs. sensorineural loss). Tympanograms/acoustic reflexes will be obtained at 1-week formal audiology follow-up. Repeat portable audiology may be performed for test-retest reliability and validity relative to lab audiology.

6.3.11 General Self-Rated Health Status: We will use two single-item general self-rated health measures to assess current health status and recent changes in health status at baseline, 1-week, and 1-month.

6.3.12 Dizziness Handicap Inventory – Screening (DHI-S¹⁶⁹): The DHI-S is a 10-item, self-reported, screening version of the full DHI and will be used to identify difficulties that the subject may be experiencing because of dizziness or unsteadiness. Subjects will complete the DHI-S at baseline, the 1-week visit and the 1-month visit.

6.3.13 Simplified modified Rankin Scale questionnaire (smRSq): The smRSq is a shorter, telephone-enabled version of the standard modified Rankin stroke-related disability score. The smRSq will be assessed at baseline and at the 1-week and 1-month follow-up visits to determine a mRS score.

6.3.14 Neuro-QoL: The Neuro-QoL is a set of self-report measures that assess health-related quality of life by evaluating symptoms, concerns, and issues that are relevant across different neurological disorders. Subjects will complete multiple short form items from the Neuro-QoL at the 1-week visit.

6.3.15 RAND 36-Item Health Survey (RAND-36¹⁶⁸ v1.0): The RAND-36 uses 36 questions to measure functional health and well-being. Subjects will complete the RAND-36 at the 1-month follow-up. This instrument is made up of the same 36 questions as the Medical Outcomes Study Short Form (MOS SF-36) but uses a different scoring algorithm (http://www.rand.org/health/surveys_tools/mos/36-item-short-form.html).

6.3.16 Charlson Comorbidity Index (CCI): The CCI is a composite scoring measure of medical comorbidity based on the presence or absence of 19 specific conditions and the patient's age. The CCI will be assessed at the ED Index Visit and updated at 1-month based on medical chart review.

6.3.17 MRI pre-screen: All patients will complete an abbreviated set of questions related to magnetic resonance (MR) pre-procedure screening during the Screening & Recruitment period to determine eligibility. Patients with known contraindications to MR imaging will be excluded from the trial. For those randomized, standard MRI pre-screening will occur per local institutional policies prior to safety (ED Index) or research (1-week) MRI.

6.3.18 MRI: ED Index Visit MRIs differ from Week-1 research follow-up visit MRIs (Table 2). To maximize trial safety, all patients in the VOG arm of the study will undergo stroke protocol (safety; 1.5 Tesla) MRI with non-contrast MRA to minimize risk that a patient is erroneously discharged with a stroke. VRT-arm subjects with suspected central lesions will be admitted for stroke care and undergo clinical stroke protocol MRI with MRA as part of the required trial care pathway. VOG care patients slated for discharge will undergo same-day safety MRI if they have not had a clinical MRI. Stroke-protocol images (for safety or based on pathway VRT-C) will not be specifically adjusted or harmonized for the research study; they will use standard clinical protocols, so as to minimize clinical disruption in the ED and radiology department. Although the protocol requests a non-contrast MRI/A (to minimize total contrast dose, in light of Week-1 contrast-enhanced MRI), the patient's clinical providers may request contrast-enhanced imaging be added if clinically indicated for patients without contraindications to contrast. All enrollees will undergo a Week-1 gold-standard (3 Tesla with or without contrast) MRI (stroke, internal auditory canal sequences pre-/post-contrast, if applicable). A 1.5 Tesla basic stroke protocol MRI will be obtained if scheduling conflicts or institutional policies prevent the use of a 3T scanner. The Week-1 MRI protocol has been optimized to include images to detect posterior fossa stroke as

well as other posterior fossa and vestibular lesions (e.g., demyelinating lesions, cerebellar tumor, acoustic neuroma). The Week-1 research MRI acquisition protocol was adapted at the start of the study for each site's MRI technology (GE vs. Siemens, 3 Tesla) by the principal study neuroradiologist. The optimal MRI window is described in 6.2.3.

The rationale for obtaining the delayed gold-standard MRI is that the sensitivity of MRI for detecting stroke is much greater at days 3-7 than in the first 72 hours after onset of symptoms. MRI sensitivity (using diffusion-weighted imaging [DWI] optimized for stroke detection) rises sharply in the first few hours after the onset of stroke symptoms. False negative scans are more frequent in the first 24 hours after onset of posterior fossa stroke symptoms than in the subsequent period from 24-72 hours after onset. MRI sensitivity is about 80%²⁹ <24 hours and about 86%⁷³ <72 hours. Maximal MRI sensitivity (~99%⁷³) is achieved after about 72 hours, and is maintained at a high level until ~14 days after onset of symptoms, then declines to a nadir around 1 month.¹⁰⁷ Accordingly, only those whose gold-standard MRI scans were obtained within the 14-day period will be included as part of the primary analysis for the main trial outcome (see Statistical Analysis Plan below).

Oral anxiolytic therapy may be offered to subjects per local institutional policy who have MRI anxiety. This will be documented in the subject's record and same-day follow-up assessments that may be affected by anxiolysis (e.g., vestibular testing) must be completed prior to anxiolytic administration.

MRIs will be read by two independent, masked study neuro-radiologists. For safety, all 1-week study MRIs will also be read clinically as an urgent ED scan by on-site clinical radiologists.

Standardization MRIs (normal volunteers, occurred only during protocol refinement phase): The MRI acquisition protocol was adapted for each of the study center's MRI technology (GE vs. Siemens, 1.5 Tesla vs. 3 Tesla) by the principal study neuroradiologist in collaboration with an MRI physicist. To ensure that MRIs for the 1-week gold standard study were harmonized across sites, the MRI personnel from the CC visited each study center and collaborated with the local MRI personnel. This process involved scans obtained from both a "phantom" (non-human or animal impregnated gel) and 1-4 human volunteer subjects (inclusive of study staff from the CC to allow for the same person(s) to undergo MRI scanning at each site to enhance MRI standardization across sites). Each volunteer underwent MRI (see Table 2 for sequences) for 60-180 minutes depending on the progress of the harmonization process. Scanner settings were adjusted during this time until optimal settings were obtained. This protocol differed from the final protocol for the patients enrolled in the AVERT Trial; no gadolinium was used, negating the need for IV access and assessment of kidney function.

Table 2. Major MRI sequences obtained as part of the standard MRI protocols in the AVERT Trial

Time Point	Stroke Images	Posterior Fossa, Internal Auditory Canal (IAC) Images	Approximate Length	Image Strength
Immediate safety MRI obtained in all VOG patients before being released from the hospital	Stroke protocol MRI (using non-contrast clinical protocol for each site, whether or not it includes an MRA)	none	30 min image acquisition time (total time ~45 min)	3.0 Tesla or 1.5 Tesla
Gold standard MRI (1 wk)	Stroke protocol MRI with diffusion-weighted, T2 FLAIR, susceptibility-weighted images for stroke Stroke protocol MRA with contrast and special T1 sequences for vertebral artery or basilar dissection	IAC protocol MRI with pre- and post- contrast images, ¹⁰⁸ including axial and coronal T1 as well as CISS sequences with thin cuts through the posterior fossa, including the vestibular (8 th) nerve complex for patients without contraindications to contrast	90 min image acquisition time (total time ~90 min)	3.0 Tesla or 1.5 Tesla
Standardization MRI (normal volunteers only)	same as above	same as above but without contrast use or post-contrast sequences	60-180 minutes	3.0 Tesla

6.3.19 Hospital admission: The ED provider determines if admission is necessary for the standard care pathway. The research team will request that the ED provider admit eligible subjects randomized to VRT whose VOG diagnosis is ‘central’ at the ED Index Visit. Those whose VOG diagnosis is ‘equivocal’ will have hospital admission determined by the ED provider in consultation with a neurologist, when available. Those whose VOG diagnosis is ‘peripheral’ will be discharged after safety MRI, unless the ED provider decides to admit ‘off protocol’ for safety.

6.3.20 Neuro-otology examination: All subjects will undergo a focused neuro-otology examination at the 1-week visit to evaluate ongoing and new clinical symptoms since the ED Index Visit, to assess the likely diagnosis, and to provide any necessary referrals or communication with other providers.

6.3.21 Laboratory-based vestibular testing: All subjects will undergo formal vestibular testing at the 1-week visit. This standard clinical vestibular testing battery (~3 hours) will include the following:

1. Subjective visual vertical (SVV) testing

This test requires the patient to re-position a mechanical light bar so it is oriented upright. Depending on site-specific procedures, this may occur using the ‘bucket test’ (described above).

2. Video-oculography (VOG) saccade accuracy testing

This test requires the patient to look from side to side.

3. Video-oculography (VOG) head impulse testing (vHIT), 6 semicircular canal planes.

This test involves ~15 rapid head rotations in the plane of each semicircular canal.

4. Video-nystagmography (VNG) with caloric testing.

This test involves a series of maneuvers designed to elicit nystagmus. These include looking side to side, blocking visual fixation, passive head shaking, positional tests (Dix-Hallpike, supine roll), and bithermal caloric testing (warm and cold water instilled into the ear canal) while supine.

5. Vestibular-evoked myogenic potentials (VEMPs), cervical (c-VEMPs) and ocular (o-VEMPs).

Both tests are performed supine and using non-invasive, surface electrodes to measure neck and eye motor responses to auditory, vibratory, or forehead ‘tapping’ stimuli. The c-VEMPs test requires patients to lift or turn their heads against resistance to activate the sternomastoid muscle; they may also be asked to clench their teeth to activate the jaw muscles and to look at a fixed target. The o-VEMPs test does not require any sustained patient effort. Tone bursts will be presented unilaterally to the test ear through a calibrated audiometric speaker or bone conduction vibrator at a varied stimulation rate to obtain thresholds for response. In order to test utricular function, VEMP responses to midline forehead taps will be measured. The stimulus consists of a brief acceleration of the head imparted to the forehead with a neurological reflex hammer or a mechanical device (a short-distance tapping instrument that can give a repeated tap at set time intervals).

SVV, VNG with caloric testing and VEMPs will be performed at all sites where clinical appointments are readily available, and at the same location as the rest of the follow up visit. Sites with logistical constraints for getting these tests will perform them on a time permitting basis at follow-up.

6.3.22 Laboratory-based audiology: All subjects will undergo formal audiology testing at the 1-week visit. Pure tone thresholds at 500 Hz through 8000 Hz will be measured in addition to speech reception threshold and speech discrimination score. Testing will be performed in a sound-proof booth with a clinical audiometer. Tympanometry (test of middle ear compliance during changes in external auditory canal pressure and during comfortable-level sounds applied by an audiometer speaker so as to assess stapedius/acoustic reflex function) will also be performed.

6.3.23 Emergency Department Patient Experiences with Care (EDPEC): An abridged version of the EDPEC survey (<https://www.cms.gov/Research-Statistics-Data-and-Systems/Research/CAHPS/ed.html>) using questions focused on overall experience will be completed by subjects at the ED Index Visit and 1-week follow-up visit to provide their perspectives on the care they received during the ED Index Visit.

6.3.24 Resource utilization: SCs will record the number and type of brain imaging studies, consultations, and admissions, as well as ED length of stay. They will note key process measures such as whether patients are treated with anti-vertigo medications or undergo specific canalith repositioning therapy.

We will track use of higher-cost services likely to be impacted by VOG care at ED visit and in follow-up (radiology/lab tests, physician consultations, admissions). Costs will be based on national average Medicare reimbursement (commonly used in cost analyses¹⁷⁰), or, as needed, average consortium costs.

6.3.25 Medical record review: Medical records will be accessed at the ED Index Visit to identify relevant medical conditions related to inclusion/exclusion parameters or critical study covariates. SCs will review medical records for baseline medical comorbidities (and any acquired during the 30-day follow-up period), ED/hospital/outpatient healthcare visits, and major medical events (falls, hip fractures, vascular events [stroke, myocardial infarction, venous thromboembolism], and test or treatment complications related to studies/interventions during the study period (ED Index through 1-month).

6.3.26 Canalith repositioning treatment for BPPV: For patients in the VRT arm with an algorithmic, VOG-derived diagnosis of BPPV, SCs will provide standard, evidence-based guideline-recommended canalith repositioning treatments.^{49,50} These maneuvers are simple and routinely performed by vestibular physical therapists and nurses in clinical practice. All SCs will be trained to provide canalith repositioning for posterior canal BPPV via the modified Epley canalith repositioning maneuver (a 270 degree rotation from the Dix-Hallpike test position). SCs with more experience will also perform horizontal canal canalith repositioning treatments (e.g., the Lempert roll maneuver, which is similar to the Epley but with the chin tucked forward rather than head hanging back). No treatments for anterior canal BPPV will be applied by SCs, as our current VOG algorithm dictates that patients with positional downbeat nystagmus are diagnosed as presumed to have central lesions until proven otherwise by neuroimaging; if this aspect of the VOG algorithm is modified during the course of the study, only SCs with adequate experience or training in treatment of anterior canal BPPV will apply the appropriate maneuvers. Our standard approach will be the one typically used in subspecialty practice: to apply the treatment maneuver up to three times or until the nystagmus has resolved on positional testing. The treatments will be provided under VOG guidance—the VOG tracks the three-dimensional position of the head in space, and notifies the user if the patient's head angles are not in the appropriate planes/locations. This will increase the accuracy of treatments by SCs with less experience. It will also provide an internal check on accuracy and effectiveness of treatment procedures, as the VOG traces and videos from the treatments will be reviewed by neuro-otologists for correct technique and correct results (based on nystagmus patterns). At any time, the ED provider may go 'off protocol' for any safety or treatment effectiveness concerns and request an ENT or physical therapy consultant to perform the maneuvers instead of (or in addition to) the SC. Similar treatments will be applied at the 1-week follow-up visit if patients have BPPV symptoms and findings.

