4.1 Inclusion criteria

Adult (18 years and older) ED patients with all of the following (all determined pre-randomization):

1. VESTIBULAR SYMPTOMS: presenting symptom of “vertigo” OR “dizziness” OR “unsteadiness” (as defined by consensus expert definitions in the International Classification of Vestibular Disorders²⁵)
2. RELEVANT EXAM SIGNS*: pathologic nystagmus (spontaneous, gaze-evoked, or positional) by bedside VOG testing OR pathologic ataxia (gait, trunk, stance, limbs) by bedside ataxia examination
3. RECENT ONSET: symptoms AND signs* appear to be new or markedly worse in the past month

* Exam signs are required for randomization, but not for the observational arm

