4.3.7 Masking (blinding): Allocation will be known to SC, ED provider(s), and patients (VOG result added to the medical record in the intervention arm), in order to guide management in the ED. This allocation will also be known to a small number of personnel at the CC, including members of the biostatistics team. The Investigator will become unmasked to allocation status for patients who have completed their final diagnosis adjudication as part of the iterative VRT algorithm refinement process (see Section 5.1.1). Since this is a diagnostic (not therapeutic) trial, masking is most crucial for outcome assessors, who will adjudicate final diagnoses ‘offline,’ masked to allocation status. Procedures will be used to ensure maximal masking of the Final Diagnosis Adjudication Committee (FDAC) members to trial allocation. In particular, all testing protocols are the same between the two arms of the study other than the required “safety MRI” in the VRT arm (Figure 1). The risk of unmasking of allocation therefore relates to patients in the standard care arm who do *not* undergo clinical MRI. The FDAC process will proceed in two discrete stages separated in time: (1) based solely on ED index visit data *without* the safety MRI; (2) based on all clinical data through the 30-day follow-up. Study radiologists will be masked to the index visit scan purpose/type (“safety MRI” vs. “pathway MRI” vs. “clinical MRI”), so the presence or absence of an imaging study will not cue them to the allocation during the first stage of FDAC review. During the second stage of review, study radiologists will reference any prior imaging studies using standard language that prevents disclosure to the other FDAC members whether a prior imaging study was or was not available (e.g., “The present study was compared to any prior studies, if available, and revealed no evidence of interval change.”). The actual FDAC review will occur approximately 1 month after these images are interpreted, so the neuro-radiologist, when reviewing this summary, will generally not recall which subjects did or did not have MRI imaging prior to the definitive, 1-week research MRI. If they do recall this information for a particular subject, they are instructed not to indicate this to the remaining FDAC members.

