6. CLINICAL AND DEVICE-BASED TESTING

6.1 Schedule of Evaluations

Test/Procedure	Screening & Recruitment	ED Index Visit & Hospitalization	1-Week* Visit Follow-up (+/- 3 days)	Phone Follow-up 30 days (+/- 7) & 6 months (+/- 1)
Consent	X			
Symptom History				
Structured Symptom History	X		X§	X§
Vertigo Symptom Scale (VSS-SF)		X§		X§
ABCD ²	X			
Neurological Examinations				
NIH Stroke Scale (NIHSS)	X		X§	
Scale for the Assessment and Rating of Ataxia (SARA)	X		X§	
Calibrated Finger Rub Auditory Screening Test (CALFRAST)	X		X§	
Subjective visual vertical (SVV)		X§	X§	
Portable VOG (HINTS-Hallpike)	X		X	
Portable audiometry (air, bone hearing)		X§	X§	
Health Status Measures				
General Self-Rated Health	X		X	
Dizziness Handicap Inventory-Screening (DHI-S)		X	X	X
Modified Rankin Scale (mRSq)		X	X§	X
Neuro-QoL (multiple short form items)			X§	
RAND 36				X§
Charlson Comorbidity Index (CCI)		X§		X
MRI pre-screen	X		X (per local policies)	
MRI		X [†] (VRT arm)	X*	
Hospital admission		X‡ (VRT-C subarm)		
Neuro-otology examination			X	
Laboratory-based vestibular testing			X§	
Laboratory-based audiometry			X§	
EDPEC (satisfaction with overall experience)		X§	X§	
Resource utilization review		X	X§	X
Medical record review	X	X	X	X
Canalith repositioning treatment for active BPPV		X (VRT-P subarm)	X	
National Death Index review				X#

* Optimal timing for the follow-up Research MRI is days 3-7 after onset of symptoms, so timing of “1-week” follow-up will be scheduled accordingly.

§ Time permitting. Time constraints may make some of the testing, especially during the ED index visit, unrealistic under certain circumstances.

† MRI required for all participants in the VRT care arm (pathway MRI in VRT-C; safety MRI in VRT-P or VRT-E) unless ordered clinically; clinical MRI may or may not be ordered by the clinical care team for participants in the Standard ED-care (control) arm.

‡ Hospitalization may or may not be ordered by the clinical care team for any patient in either arm, but is pre-specified in the VRT-C subarm.

For patients lost to follow-up at 6 months, we will search the National Death Index to ascertain their vital status and cause of death, if available.

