Secondary analysis 1: For each of the six possible diagnosis categories (3 peripheral, 1 central, 1 medical/other, 1 non-diagnosis), define the gold standard =1 if the 30-day adjudicated final diagnosis is the corresponding category and 0 otherwise. Define test positive respectively for “Index VRT Diagnosis” and “ED SOC Diagnosis” if the diagnosis is the corresponding category and 0 otherwise. Estimate sensitivity, specificity, predictive values and likelihood ratios accordingly for “Index VRT Diagnosis” and “ED SOC Diagnosis”. Between-arm comparisons will be performed by the generalized linear model with a log link as described in primary analysis 1a.

Tertiary analysis 1: Subgroups and covariates:

The regression model is

$$\log TPR(X_{Test}) = \alpha_0 + \alpha_1 X_{Test} + \overline{\alpha_l} \cdot \overline{X_l}$$

where $\overline{X_l}$ is a vector of additional subgroup variables or other covariates to be explored for assessing the influence of demographic and key clinical variables described below.

1) Potential Subgroups:

- a. AVS-Only Group: using only patients with acute (continuous) vestibular syndrome >24hr.
- b. Younger-Patient Group: using only patients 49 years of age or younger (i.e., 18-49).
- c. Women-Minority Group: using only patients self-identifying as female, minority, or Hispanic.
- d. NIHSS 0 Group: using only patients with an NIH stroke scale score of zero at ED index visit.
- e. Stands-Independently Group: using only patients who stand without assistance or support.
- f. Normal Hearing Group: excluding any patient with hearing loss (new or old).
- g. Non-AICA Group: excluding any patient with an AICA-territory stroke diagnosis.
- h. Pre-Treatment Group: using only patients with results obtained prior to anti-vertigo meds.
- i. VRT Definite-Only Group: using only “definite” VRT diagnoses (excluding VRT-E cases).
- j. Specific ED-Only Diagnosis Group: using only “definite” ED diagnoses (excluding ED O2).
- k. Neuro-otologic Diagnosis Group: using only patients with peripheral or central diagnoses.

2) Potential Covariates:

- l. Site: JH vs. UI vs. UM.
- m. Age (ordinal): 18-49, 50-59; 60+ years.
- n. Age (continuous): for each year.
- o. Sex: female vs. male.
- p. Race/Ethnicity: minority vs. non-Hispanic white.
- q. Symptom Onset (ordinal): 0-24, 25-48, 49-72, >72 hours.
- r. Symptom Onset (continuous): time from symptom-onset for each hour.
- s. Symptom Type: vertigo vs. dizziness vs. unsteadiness.

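### NIHSS and SARA may first be scored after randomisation with no masked scorer named, so exploratory subgroup (d) and covariates (x) and (y) may not be true baseline values

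*Protocol*

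**What the plan says.** **Timing of NIHSS and SARA.** On NIHSS, Protocol 6.3.5 reads: "The NIHSS will be done by a certified examiner during screening or shortly after randomization and then repeated at the 1-week visit". On SARA, 6.3.6 reads: "The SARA evaluation will be done during screening or shortly after randomization and then repeated at the 1-week follow-up visit". The Schedule of Evaluations (Protocol 6.1) marks the first scoring of both under Screening & Recruitment and has no mark for either under the ED index visit.

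**Masking.** Protocol 4.3.7 states: "Allocation will be known to SC, ED provider(s), and patients". The masking measures there concern the adjudicators and study radiologists. Protocol 4.3.2 makes the coordinator responsible for collecting clinical data. For NIHSS, 6.3.5 asks only that the examiner be certified.

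**VSS-SF.** Protocol 6.3.3 calls the first VSS-SF a baseline measure. The schedule shows it only under the ED index visit, with a footnote that it is done if time allows: "Time constraints may make some of the testing, especially during the ED index visit, unrealistic under certain circumstances". Protocol 6.2.2 starts that phase on the day of randomisation, and 5.1.2 says that further research data are gathered after randomisation.

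**Use.** SAP 2.2.1, Tertiary analysis 1, lists subgroup (d): "NIHSS 0 Group: using only patients with an NIH stroke scale score of zero at ED index visit". VSS-SF, NIHSS and SARA are potential covariates (t), (x) and (y). Protocol 9.2.1 has the same list, and Aim 3 draws on it for its models.

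**The concern.** A subgroup or adjustment variable in a randomised comparison should be fixed before the arm is known. If it is scored afterwards by someone who knows the arm, and in the VRT arm possibly the VOG result, the score can depend on allocation. Membership of subgroup (d) could then differ between arms for reasons unrelated to the patients, and randomisation would no longer protect that comparison or a model adjusted for (x) or (y).

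The SAP does not close the gap. It ties subgroup (d) to the ED index visit, but Protocol 5.1.2 treats screening as the early part of that visit, so the label covers both sides of randomisation. No rule limits the analysis to scores taken before allocation.

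VSS-SF raises a related point. It is reported by a patient who knows the arm once randomised, nothing requires it to precede allocation, and it may be skipped. A model that includes it may use a value taken after allocation, or lose patients.

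**Working it through.** **1. Text against schedule.** For NIHSS and SARA, 6.3.5 and 6.3.6 allow two times (screening, or soon after randomisation), and the schedule allows one (screening). A site following the text can record a first score after allocation without deviating from it. For VSS-SF, 6.3.3 says baseline, while the schedule column and 6.2.2 point to the period from randomisation onward.

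**2. The plan's sample size, for reference.** Inputs from SAP 2.3: 90% vs 75%, alpha 0.05 (taken as two-sided), power 80%.
- Uncorrected: n0 = [1.960·√(2·0.825·0.175) + 0.842·√(0.90·0.10 + 0.75·0.25)]² / 0.15² = 99.5, rounded up to 100.
- Continuity-corrected: n = (n0/4)·[1 + √(1 + 4/(n0·0.15))]² = 112.5, rounded up to 113, the stated figure.

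Nothing in this calculation uses NIHSS, SARA or VSS-SF, so 113 per arm stands.

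**3. Possible bias in subgroup (d), by illustration.** Assume no true difference between arms. Let s be the stroke share (10-20%, SAP 2.3), a_s the accuracy in stroke (50-70%, the SAP's figures for routine ED care, applied here to both arms), a_n the accuracy in non-stroke (75-90%, borrowed from the planning proportions), and q the share of VRT-arm strokes moved above NIHSS 0 because the arm and result are known (25-50%, assumed). All strokes are taken as truly NIHSS 0, an upper bound.
- Bias = [s(1-q)a_s + (1-s)a_n] / [s(1-q) + (1-s)] - [s·a_s + (1-s)a_n].
- Smallest (s = 0.10, a_s = 0.70, a_n = 0.75, q = 0.25): +0.1 points.
- Largest (s = 0.20, a_s = 0.50, a_n = 0.90, q = 0.50): 0.77/0.90 - 0.82 = +3.6 points.

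Now suppose that only correctly called strokes are moved out, with accuracy a = 90% throughout.
- Bias = [s·a(1-q) + (1-s)a] / [s·a(1-q) + s(1-a) + (1-s)] - a.
- s = 0.10, q = 0.25: 0.8775/0.9775 - 0.90 = -0.2 points.
- s = 0.20, q = 0.50: 0.81/0.91 - 0.90 = -1.0 points.

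The sign depends on which patients are rescored, and the documents do not settle that.

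**4. Loss of patients if VSS-SF enters a complete-case model.** The documents give no missing rate. At an assumed 20-40%, the loss is 0.20·226 = 45 to 0.40·226 = 90 patients. Power for 90% vs 75%, approximated by the two-proportion test on those retained, is Φ{[0.15 - 1/n - 1.960·√(0.28875/n)] / √(0.2775/n)}.

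| Missing | n per arm | Power |
|---|---|---|
| 0% | 113 | 80.2% |
| 10% | 102 | 75.3% |
| 20% | 90 | 69.4% |
| 30% | 79 | 62.5% |
| 40% | 68 | 54.6% |

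This applies only to an optional model containing VSS-SF.

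**The case against.** The strongest reply is that little of importance rests on these scores. Without covariates the primary test is the Pearson chi-square (SAP 2.2.1). Subgroup (d) and the covariates are potential items under a tertiary analysis, and no adjusted Aim 1 analysis is committed to. This stands, and it sets the severity.

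A reader might infer that eligibility is compromised. The documents do not show that. Protocol 4.1 opens: "Adult (18 years and older) ED patients with all of the following (all determined pre-randomization". Its exam sign is nystagmus on VOG or ataxia on a bedside ataxia examination. SARA is not named there, and no criterion uses NIHSS or VSS-SF. SARA is the only ataxia scale in the schedule, but equating it with the eligibility examination is inference.

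A reader might also infer that the VRT result could colour the Aim 3 models. Those models use the standard-care arm only, where no VOG report is generated. Only timing and missing values matter there.

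The exposure is also partly inferred. The NIHSS examiner need not be the coordinator. Expert review in the VRT arm takes about 10-15 minutes (Protocol 5.1.3), so the result may not yet be available when a score is taken soon after randomisation. Repositioning by coordinators is limited to VRT-arm patients with a VOG diagnosis of BPPV, and nothing says that it precedes VSS-SF. These points make bias less certain, but they do not remove the option to score after allocation or supply a masked scorer.

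**Conclusion.** The point holds as a low-severity, cheap improvement. The text on NIHSS and SARA conflicts with the schedule. Followed as written, it can put scores taken after allocation, by people not stated to be masked, into an exploratory between-arm subgroup and optional adjusted models. VSS-SF may likewise be recorded after allocation, or be missing.

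The size and direction of any bias are unknown. The range of about -1.0 to +3.6 points rests on assumed rescoring rates and on every stroke patient truly scoring NIHSS 0. Claiming a systematic advantage for VRT would go too far. So would claiming harm to the unadjusted primary comparison, the sample size or eligibility. Missing VSS-SF that differs by arm is possible but not shown.

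**What to change.** - **Protocol 6.3.5 and 6.3.6:** reconcile with the schedule so that the first NIHSS and SARA are scored before randomisation.
- **SAP 2.2.1:** state that subgroup (d) and covariates (x) and (y) use only scores time-stamped before randomisation, and that later scores count as missing.
- **VSS-SF:** use it in between-arm models only where it was recorded before randomisation, or drop it from that list. For Aim 3, report when it was taken and how often it is missing.
- **Optional:** one sentence stating whether SARA is the ataxia examination meant in Protocol 4.1.

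The cost is wording, plus either slightly longer screening or a few missing scores in exploratory models. The schedule already places NIHSS and SARA in screening, which 5.1.2 puts at about 30-45 minutes, although no section confirms that both fit within that time. If sites find the order unworkable during clinical care, the SAP restriction alone keeps late scores out of the between-arm analyses.
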